3. Alcohol consumptions (AUDIT-C)
4. Stress, measured by means of the Perceived Stress Scale, 4-item
5. Medication Adherence, measured by how many days/weeks the recommended medications are taken, reported by the patient
6. Healthcare access, patients' report on where they normally seek medical care.

After informed consent is obtained, assignment will be unveiled to the participant by the consenting research assistant and the participant will be assigned also with an ID number which will be used in all

procedures using de-identified data.

Participants assigned to the Usual Care (UC) group will be treated using best practice evidence-based discharge procedures, involving a team-based approach to enhance coordination of care for individuals at high risk for readmission.

Participants assigned to the Mi Puente group will be receiving usual care along with the Mi Puente discharge procedure. The latter involves individualized support from a Behavioral Health Nurse while inpatient, a follow-up call from the Behavioral Health Nurse during post-discharge week 1 and weekly supportive phone calls from a Volunteer Peer Mentor during post-discharge weeks 1-4. The intervention will focus on building resources, skills, knowledge and on empowering patients and connecting them with appropriate outpatient services.

EMR of all study subjects will be audited for specific information relevant to the trial (e.g. diagnoses, medication, complications, readmissions, length of stay) at baseline and for readmissions at 30-days and 180-days after baseline.

All study subjects will participate in three assessments of approximately 30-60 minutes duration at baseline and at 3 months and 6 months after baseline. Baseline assessment will be performed prior to hospital discharge in person and the month-3 and month-6 assessments will be conducted by telephone.

Data collected during these assessments will involve the following patient-reported indicators:

1. Demographic information (study-specific/standard item)
2. Physical symptoms, measured via the PHQ-15
3. Quality of life, measured by the PROMIS General Health Scale
4. Healthcare access and barriers, measure adapted from the HCHS/SOL
5. Patient activation, measured by the Patient Activation Measure
6. Support resources for disease management, measured by means of the Chronic Illness Resources Survey.

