Guided by the RE-AIM framework, the program evaluation will examine the success of Mi Puente versus Usual Care in 1) Reaching a representative segment of the population (Reach); 2) Achieving meaningful outcomes through a well-implemented intervention (Efficacy/Implementation); and 3) Creating an intervention that can be adopted by and maintained in a real-world environment (Adoption/Maintenance). As part of the evaluation, 20 participants will be invited to attend focus groups to share their experiences with the intervention (2-3 groups). The Behavioral Health Nurse and Volunteer Peer Mentors will also serve as “participants” via their involvement in evaluating the treatment fidelity of and their experiences with Mi Puente.

Cost-effectiveness Analysis (CEA) of the Mi Puente intervention relative to Usual Care only will be conducted focusing on services delivered by the two care partners (Scripps/San Ysidro Health center) and Mi Puente coordination over the 6-month study period. Cost-effectiveness will be estimated using the Incremental Cost Effectiveness Ratio (ICER). The estimated ICER will be compared to CEA standards

and similar interventions to provide context for the cost-effectiveness of Mi Puente.

Timeline: The study will be conducted over 5 years, 07/01/15 – 06/30/20. The first 6 months will be devoted to start-up. Eligible patients will be enrolled between months 7 and 46 and the recruitment target is approximately 28 patients per month during this period, with post-discharge telephone intervention for Mi Puente group participants concluding in month 47. Follow-up telephone assessments of patient-reported outcomes will be completed between months 10 and 52. Focus groups will follow in months 53-54 and the last 6 months will be devoted to statistical analyses and report preparation.

Study participants will be offered gift cards as an incentive to complete all assessments. Study participants will receive compensation after baseline (\$20), month-3 (\$20) and month-6 (\$25) assessments in the form of gift cards. The total incentive for participants who will complete all assessments will be \$65. Gift cards will be given after completion of each assessment; that is at baseline, 3-months and 6 months.

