Patients interested in the study will be approached by a trained bilingual staff member while inpatient. The bilingual staff member will introduce the study to the participant and obtain verbal consent to administer evidence-based behavioral health screening. Patients who are deemed eligible to participate in the study will be provided with a copy of the consent form and will review all content together with the staff member both in Spanish and English. Adequate opportunity will be provided to the potential participant to consider all options and ask questions; care will be taken to ensure that all participants understand the information and that their participation is voluntary. Prior to each follow-up appointment, research staff will remind participants of the procedures and the voluntary nature of their participation.

Statistical Analysis Plan

Sample size

Power and Sample Size

The target study sample size is 560 participants allocated equally to the two groups ($n = 280/\text{group}$). Sample size estimates were calculated based on the primary outcome of hospital utilization at 30 and 180 days, and the secondary outcome of changes in patient-reported outcomes. All estimates were generated using RMASS2 assuming a statistical significance level of .05 (two-tailed), and targeting at least 80% power. Sample size estimates were adjusted to up to 20% total attrition. Power analyses indicated that a sample size of 558 is needed at baseline to find a statistically significant incidence rate ratio of expected magnitude with 80% power. For patient-reported outcomes, we estimated an effect size of $d = 0.50$ as a clinically significant change. Using parameters defined above, 280 participants are needed to find a statistically significant difference between groups.

Analytic Plan

All analytic strategies will follow intent-to-treat principles. Preliminary data screening and cleaning will be conducted, and statistical testing and effect size consultation will be used to determine if random assignment has resulted in statistical equivalence between groups. Significant covariates will be added to adjust for nonequivalence. Analyses of hospital utilization (primary outcome) and patient-reported

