outcomes will be conducted using multi-level modeling and the appropriate link function for a target outcome. Analyses will include “group” (Mi Puente or Usual) as the between-subjects factor, “time” (assessment dates) as the within-subjects factor, and a cross-level, “group-by-time” interaction effect. Analyses will be conducted in IBM SPSS Statistics 22.0 (IBM, Inc., Armonk, NY, UK) and MPLUS (Muthen & Muthen, Los Angeles, CA, USA). Effect size indicators and confidence intervals will also be examined and reported.

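### Does the SAP leave open when the 30- and 180-day windows of its primary outcome begin?

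*Combined protocol and SAP*

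**What the plan says.** The start of the windows and the time factor are covered in four places.

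- **Mi Puente Protocol, paragraph on the record audit.** Records of all participants are audited at baseline and then "for readmissions at 30-days and 180-days after baseline".
- **Mi Puente Protocol, paragraph on assessments.** Participants have "three assessments of approximately 30-60 minutes duration at baseline and at 3 months and 6 months after baseline". On timing: "Baseline assessment will be performed prior to hospital discharge in person". The two later contacts are by telephone, and the six indicators listed for the assessments are all patient-reported.
- **SAP, Power and Sample Size.** The sample size rests on the "primary outcome of hospital utilization at 30 and 180 days", with no start point given.
- **SAP, Analytic Plan.** One model description covers both outcome families ("Analyses of hospital utilization (primary outcome) and patient-reported" outcomes). Its time factor is worded "assessment dates) as the within-subjects factor", and the link function is chosen to suit the outcome.

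The nurse and peer-mentor calls are timed from discharge. The Timeline paragraph says "Eligible patients will be enrolled between months 7 and 46", with the post-discharge "telephone intervention for Mi Puente group participants concluding in month 47".

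**The concern.** Three features together suggest that the primary outcome is not pinned down.

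1. The audit clock starts at baseline, during the index stay, when a readmission is not yet possible. The intervention calls run on a different clock, from discharge.
2. The SAP gives 30 and 180 days without an origin and does not refer back to the audit paragraph. That paragraph speaks of readmissions, whereas the SAP speaks of hospital utilization.
3. The protocol uses the word assessment for the contacts at baseline, 3 months and 6 months. Read literally, the SAP's time factor would put the first follow-up point for hospital utilization at about 91 days, not 30.

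If the origin were truly open, two different 30-day counts could each be called the primary result. Choosing between them after seeing the data would raise the false-positive rate. A baseline origin also leaves slightly less post-discharge time at risk, and so fewer events, than a discharge origin.

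**Working it through.** **The plan's own figure.** The SAP gives 558 participants for the incidence rate ratio. It cannot be reproduced, because the rate ratio, control event rate and dispersion are not stated. It therefore cannot show which origin was assumed. All that follows is 558 × 0.8 / 2 = 223.2 evaluable per arm after 20% attrition.

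**Which origin the document supports.**

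| Item | Clock | Source |
|---|---|---|
| Readmission audits, 30 and 180 days | baseline | Protocol, record audit |
| Primary outcome, 30 and 180 days | not repeated | SAP, Power and Sample Size |
| Patient-reported contacts, 3 and 6 months | baseline | Protocol, assessments |
| Intervention calls, weeks 1 to 4 | discharge | Protocol, intervention |

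The primary outcome shares both its time points with the audits, which are the only scheduled source of readmission data. Discharge is used only to time the intervention. The document states one origin and no rival.

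**Which dates form the time factor.** Taking the 3-month contact as the first time point for hospital utilization would require an outcome measured then. No readmission audit is scheduled at 3 months, none of the six indicators listed for the contacts is hospital utilization, and the SAP fixes the outcome at 30 and 180 days. The ratio 91/30 = 3.03 therefore measures a reading that the rest of the document contradicts. The reading that fits every section is that each outcome is modelled at its own measurement dates.

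**Size of the baseline-to-discharge gap.** The gap s is not given. The Timeline offers a rough guide: counting July 2015 as month 1, month 46 ends on 30 April 2019. Adding s days and then 28 days of calls gives 31 May (month 47) at s = 3 and 1 June (month 48) at s = 4. This is month-level planning, not a rule, so a 7-day gap is shown as well.

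Formulas, with T the window in days:

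- share of the window before discharge = s/T
- correlation of the two test statistics = √(1 − s/T), because the count from baseline is nested in the count from discharge (constant Poisson rate and equal gaps assumed)
- two-sided error if the better of two 5% tests is reported = P(|Z₁| > 1.96 or |Z₂| > 1.96), bivariate normal

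| T | s | Share before discharge | Correlation | Error if origin picked afterwards |
|---|---|---|---|---|
| 30 | 1 | 3.3% | 0.983 | 5.85% |
| 30 | 2 | 6.7% | 0.966 | 6.20% |
| 30 | 3 | 10.0% | 0.949 | 6.48% |
| 30 | 7 | 23.3% | 0.876 | 7.3% |
| 180 | 1 | 0.6% | 0.997 | 5.35% |
| 180 | 2 | 1.1% | 0.994 | 5.49% |
| 180 | 3 | 1.7% | 0.992 | 5.60% |
| 180 | 7 | 3.9% | 0.980 | 5.9% |

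The last column describes a comparison at one time point, not the planned multilevel model, and applies only if the origin is chosen after results are seen.

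**Power.** Suppose 558 had assumed 30 full post-discharge days and events were proportional to time at risk. Power would then be Φ((1.960 + 0.842)·√((30 − s)/30) − 1.960), which is about 79% at s = 1, 76% at s = 3 and 69% at s = 7, against 80%. The supposition cannot be checked, so these figures are illustrative.

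**The case for a change.** The strongest case for acting is that the window of a primary outcome should be settled before data are seen, and that this takes only a sentence or two. The audit sentence could be read as a chart-review schedule for readmissions, not as the definition of hospital utilization. The sentence on assessment dates is the only one that defines the time factor for the primary analysis. In addition, inpatient nurse support comes after assignment is disclosed, so equal gaps are plausible but not guaranteed. With a gap of 3 days or more, a 30-day window from baseline closes before the peer-mentor calls end (28 + 3 = 31).

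Part of this stands. The SAP does not repeat the baseline origin and does not expressly tie its time factor to the audit dates. The rest does not lead to a change. Unequal gaps are a possibility for which the documents give no evidence. The overlap with the call schedule is a consequence of a defensible origin. Counting from discharge has drawbacks of its own: it starts the clock at an event after assignment and gives no window to a patient who dies before discharge. By the planned timeline enrolment opened in January 2016, before this document's date of January 2017, so it could also be a mid-enrolment change. Counting from the other origin and tabulating days to discharge by arm are optional extras, and the first needs a discharge date that the audit paragraph does not list.

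**Conclusion.** The concern does not call for a change. Read as one document, the plan gives the origin (baseline) and the dates (30 and 180 days) for the primary outcome. What is missing is a cross-reference from the SAP to the audit paragraph, together with loose wording of a time factor shared by two outcome families. Analysts can fill both sensibly, and confirming baseline would alter neither the audit schedule nor the outcome.

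The practical cost of the baseline origin is a small loss of time at risk, mainly at 30 days: up to 10.0% for an assumed gap of 3 days, against 1.7% at 180 days. The loss would be larger for longer stays after enrolment. No bias between arms is shown. This rests on two assumptions: that the gap is short, since the documents do not state it, and that it is similar in both arms.

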Cover Page for ClinicalTrials.gov

Document:

Protocol and Statistical Analysis Plan

Official Study Title:

Mi Puente: My Bridge to Better Cardiometabolic Health and Well-Being

NCT#

NCT02723019

Document Date

January 24, 2017

Mi Puente Protocol

The proposed randomized controlled trial will enroll 560 individuals according to the inclusion and exclusion criteria that follow and randomly assign them to a study group in order to test the effectiveness of Mi Puente, a nurse and volunteer peer team intervention (n=280) versus Usual Care, a best practices comparison (n=280) in Hispanics with multiple chronic physical and behavioral conditions.

Inclusion criteria:

1. Hispanic ethnicity (any race)
2. Is currently inpatient at Scripps Mercy Hospital Chula Vista
3. Age 18 years and older
4. Two or more cardiometabolic conditions (e.g., obesity, diabetes, hypertension, ischemic heart disease, congestive heart failure, other chronic coronary conditions, dyslipidemia)
5. One or more behavioral health concern(s) (e.g., broadly defined and related to mental health, medication adherence, life stressors, healthcare use, substance use)
6. Access to telephone (mobile or landline)

Exclusion criteria:

1. Pregnancy
2. Serious life-threatening condition with life expectancy <6 months.
3. Psychiatric morbidity or neurological/cognitive impairment of sufficient severity to preclude participation in the intervention.
4. Plans to discharge to location other than home (e.g., inpatient rehabilitation or nursing care)
5. Does not speak Spanish or English

Patients who are potentially eligible (based on demographics, diagnoses) will be identified through a daily review of electronic medical records (EMR) and asked by their bedside nurse if they are willing to discuss the study with research staff. Those who agree will be approached by a trained bilingual research assistant, who will obtain verbal informed consent and administer an evidence-based behavioral health screener. Patients with one or more behavioral health needs identified either via screening or EMR review (e.g. documented, pre-existing mental health diagnosis) will be deemed eligible, provided with a detailed description of the study and if interested will be asked to provide written informed consent.

Behavioral Health Screener will comprise of the following parameters:

1. Emotional Well-being, measured by the PROMIS Anxiety and Depression forms,
2. Smoking, measured by number of cigarettes smoked per day

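### Does a recruitment target of about 28 patients a month over months 7 to 46 conflict with a planned total of 560?

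*Combined protocol and SAP*

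**What the plan says.** The total is stated twice and consistently. The protocol's opening paragraph says "The proposed randomized controlled trial will enroll 560 individuals", with 280 in each group. The SAP, under Power and Sample Size, says "The target study sample size is 560 participants allocated equally to the two groups".

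The accrual schedule appears once, in the protocol's Timeline paragraph. It reserves a start-up period ("The first 6 months will be devoted to start-up") and then states: "Eligible patients will be enrolled between months 7 and 46 and the recruitment target is approximately 28 patients per month during this period". The same paragraph ends the telephone intervention in month 47 and places the follow-up assessments in months 10 to 52.

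Two other places bear on what the 28 might count. The recruitment description after the eligibility criteria sets out several steps before written consent: record review, a request by the bedside nurse, approach ("Those who agree will be approached by a trained bilingual research assistant"), verbal consent, the behavioural screener, and a decision on eligibility. The later consent paragraph likewise begins before enrolment: "Patients interested in the study will be approached by a trained bilingual staff member while inpatient". Neither gives a monthly count or the proportion expected to go on to enrol.

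**The concern.** The Timeline sentence opens with eligible patients being enrolled and then gives a monthly target for the same period. The natural reading is that about 28 patients are enrolled each month. Over 40 months that is twice the planned sample.

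If the rate were meant literally as enrolments, a trial exactly on course for 560 by month 46 would appear to be running at half its target. Someone relying on the 28 would instead expect recruitment to finish long before month 46. A reader could also wonder whether the total of 560 is right, which would matter far more, because the total carries the power statement.

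**Working it through.** **Inputs.** Total 560 (protocol opening paragraph; SAP, Power and Sample Size). Enrolment window months 7 to 46, and rate about 28 a month (protocol, Timeline). Baseline requirement 558 and attrition of up to 20% (SAP, Power and Sample Size).

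**Step 1: try to reproduce 560 as rate x months.**

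| How the window is counted | Months | 28 x months | Ratio to 560 | Rate that gives 560 |
|---|---|---|---|---|
| Both end months included | 46 - 7 + 1 = 40 | 1,120 | 2.00 | 14.0 |
| Elapsed months | 46 - 7 = 39 | 1,092 | 1.95 | 14.4 |
| Both end months excluded | 38 | 1,064 | 1.90 | 14.7 |

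The figure of 560 is not reproduced under any count. Six months of start-up make month 7 the first enrolment month, so 40 is the proper count.

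**Step 2: rounding.** If approximately 28 means 27.5 to 28.5, 40 months give 1,100 to 1,140, and 39 months give 1,073 to 1,112. Rounding does not explain the gap.

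**Step 3: attrition.** The SAP says "Sample size estimates were adjusted to up to 20% total attrition" and then "Power analyses indicated that a sample size of 558 is needed at baseline". The 558 is therefore a baseline figure with losses already allowed for, and 560 exceeds it by two. Losses after enrolment give no reason to enrol 1,120.

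**Step 4: which combinations do agree.**
- Keep total and window: 560 / 40 = 14 a month, or 7 per group.
- Keep total and rate: 560 / 28 = 20 months, that is months 7 to 26.
- Keep all three, with the 28 counted before written consent: 560 / 1,120 = 50% would have to enrol. The documents state no such proportion.

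**Step 5: do the other dates identify the error?** 7 + 3 = 10, 46 + 1 = 47 and 46 + 6 = 52 all match the Timeline. These dates are the window shifted by the follow-up and intervention periods. They show that the window was carried through consistently, but they are not independent evidence for it.

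**Step 6: where is the rate used?** Only in the Timeline sentence. The sample size rests on an incidence rate ratio, a two-sided 5% level, 80% power and the attrition allowance. The analysis uses group, time and their interaction. Neither involves the speed of accrual, and the documents describe no interim look, stopping rule or funding decision that depends on it.

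**The case for a change.** The strongest case for acting is that a monthly target exists to judge progress, and this one misleads by a factor of two on its plainest reading. The study starts on 07/01/15, so month 7 is January 2016 and the first twelve enrolment months end in December 2016, just before the document's date of January 24, 2017. At 28 a month, 28 x 12 = 336 would be expected by then; at 14 a month, 14 x 12 = 168. The reading as a count of patients approached or screened is also strained: the sentence speaks of eligible patients being enrolled, and the recruitment description makes eligibility a result of screening. The remedy would be one number or one label.

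Most of this stands. The arithmetic is right, and enrolled is the more natural reading. Two parts do not carry through. First, the documents do not show that the rate is the wrong figure. The 28 is exactly the rate for a 20-month window, and it could also refer to eligible patients who have not yet given written consent. Replacing 28 with 14 would be a guess, although changing one rate is simpler than moving several dates. Second, the harm is confined to how a progress report would look. No rule turns a shortfall against 28 into an action, and staff who know the target of 560 and the closing month can work out the pace they need.

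**Conclusion.** The inconsistency is real but has no statistical consequence. Read as enrolments, 28 a month over 40 months gives 1,120 against 560, a ratio of 2.00 (1.90 to 1.95 under the shorter month counts). The 560 itself is not in doubt from this comparison: it appears in both the protocol and the SAP and sits beside the 558 from the power analysis. The 558 cannot be recomputed, because the documents give neither the incidence rate ratio nor the base rate, but this point does not depend on it.

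No change follows. Executed as written, the plan enrols 560, allocates 280 to each group and analyses them in the same way, whether the 28 is a slip for 14, belongs to a shorter window, or counts patients before consent. Saying what the 28 counts and giving an enrolment proportion would supply operational detail without improving any estimate, test or conclusion. This rests on two assumptions: that recruitment is governed by the total of 560 and not by the monthly rate, and that no accrual-based decision rule exists outside the documents.

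### Adjustment covariates are chosen by testing chance baseline imbalance, so the primary utilization model is not fixed in advance and prognostic factors are usually left out

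*Combined protocol and SAP*

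**What the plan says.** The SAP, under Analytic Plan, states that "statistical testing and effect size consultation will be used to determine if random assignment has resulted in statistical equivalence between groups", and then: "Significant covariates will be added to adjust for nonequivalence". The next sentence introduces the models for hospital utilization (primary) and patient-reported outcomes, so the rule governs the primary model.

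The model has group, time and group-by-time terms. Its description reads in part "assessment dates) as the within-subjects factor, and a cross-level", followed by the interaction. No baseline covariate is among the terms, and the plan does not say which term carries the primary test. The Power and Sample Size section points to a rate ratio: the sample is sized "to find a statistically significant incidence rate ratio of expected magnitude with 80% power".

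The only significance level in the SAP belongs to the sample size estimates: "assuming a statistical significance level of .05 (two-tailed), and targeting at least 80% power".

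The protocol collects ample baseline information. It has a six-part screener ("Behavioral Health Screener will comprise of the following parameters"), a chart review ("audited for specific information relevant to the trial (e.g. diagnoses, medication, complications, readmissions, length of stay) at baseline") and six patient-reported domains ("Data collected during these assessments will involve the following patient-reported indicators").

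**The concern.** In a properly randomized trial any baseline difference between arms is chance. A test of balance therefore says nothing about whether a variable predicts readmission, which is what makes adjustment useful. A strong predictor that happens to be balanced is left out, and an irrelevant variable that happens to be unbalanced goes in.

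The rule is also incomplete. It names two criteria, a test and an effect size. It gives no threshold for the second, no list of variables, and no instruction for when the two disagree. Two analysts following it in good faith could fit different primary models, and neither model is known until data have been seen by arm. What is at stake is a reproducible primary analysis and, depending on the primary term, some precision that data already collected could supply.

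**Working it through.** **1. The plan's own figure.** The stated need is 558 at baseline, or 558 × 0.8 = 446 after 20% attrition. It cannot be reproduced, because the rate ratio, event rate, dispersion and within-person correlation are not given. This point does not depend on it.

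**2. How often a given factor enters.** With 280 per arm, a chance standardized difference has SD √(2/280) = 0.0845. The entry probability at cut-off c is 2[1 − Φ(c/0.0845)]. The cut-offs are assumptions, since the SAP states none for this step.

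| Cut-off | Enters | Left out |
|---|---|---|
| p<.05 (\|d\| above about 0.166) | 5% | 95% |
| \|d\|>0.1 | 23.7% | 76% |
| \|d\|>0.2 | 1.8% | 98% |

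These hold whether or not the factor is prognostic.

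**3. How much the covariate list can vary (illustrative only).** The protocol's lists give 6 + 5 + 6 = 17 items. With 17 independent items tested at p<.05, the chance that at least one enters is 1 − 0.95^17 = 58%; with 10 items it is 1 − 0.95^10 = 40%. At an assumed pairwise correlation of 0.5, simulation gives 38% and 28%. For 17 independent items the list differs between p<.05 and |d|>0.2 with probability 1 − [1 − (0.050 − 0.018)]^17 = 42%, and between p<.05 and |d|>0.1 with probability 1 − [1 − (0.237 − 0.050)]^17 = 97%. With 10 items at correlation 0.5 the figures are 23% and 80%. They describe differing covariate lists, not differing conclusions.

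**4. Validity.** In null simulations of the count model, type I error under the p<.05 rule was 4.4–5.4% (Monte Carlo SE 0.4). The mean absolute chance imbalance is 0.0845 × √(2/π) = 0.067 SD. For a covariate with rate ratio 1.3 or 1.5 per SD it shifts the estimated rate ratio by exp(0.067 × ln 1.3) − 1 = 1.8% or exp(0.067 × ln 1.5) − 1 = 2.8%. Such shifts average zero over randomizations, and the confidence interval covers them.

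**5. Precision if the primary test is the group rate ratio over follow-up.** Assumed inputs: 280 × 0.8 = 224 per arm; negative binomial totals; group rate ratio 0.567–0.700, set for about 80% unadjusted power; one covariate with rate ratio 1.3, 1.5 or 1.8 per SD; 4,000 runs per scenario. Each cell gives results in the order 1.3 / 1.5 / 1.8.

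| Events per patient, dispersion | Adjusted/unadjusted SE | Power %, p<.05 rule | Power %, always adjusted | Gain, points |
|---|---|---|---|---|
| 0.5, 0.5 | .989 / .975 / .949 | 81.8 / 80.3 / 80.8 | 82.6 / 82.2 / 84.7 | 0.8 / 1.9 / 3.9 |
| 0.5, 1.0 | .991 / .979 / .958 | 80.3 / 81.0 / 81.5 | 81.2 / 82.7 / 84.8 | 0.9 / 1.7 / 3.2 |
| 1.0, 0.5 | .981 / .957 / .917 | 80.7 / 81.9 / 83.2 | 82.2 / 84.9 / 89.7 | 1.5 / 3.0 / 6.4 |

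Gains come from unrounded values, with Monte Carlo SE 0.3–0.5 points. Against a |d|>0.1 rule the gain is 0.5–4.0 points.

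**6. Precision if the primary test is group-by-time.** In a two-period count model with gamma frailty, the likelihood splits into a part for each patient's total and a binomial part for how the total divides between periods. A time-invariant patient covariate drops out of the second part, which carries the interaction. Fitted by maximum likelihood, the adjusted/unadjusted SE ratio is 1.0000 with complete periods. With 20% missing the second period it is 0.9992, 0.9977 and 0.9959 at 1.3, 1.5 and 1.8 per SD. The gain is essentially nil.

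**The case against.** The strongest reply is that little harm follows. A simulation with 17 independent items, 1 or 3 of them prognostic at 1.3 or 1.5 per SD, looked at the primary result and not the covariate list. At about 78–86% power, the significance verdict differed between p<.05 and |d|>0.2 in 0.9–2.2% of trials, and between p<.05 and |d|>0.1 in 3.0–5.9%. The median change in the rate ratio was 0% and 1.3–2.2%. This stands: a different covariate list seldom means a different conclusion.

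The item count is also soft. The chart-review list is only an example, demographics is a domain of several variables, the emotional well-being item covers both anxiety and depression, and healthcare access appears in two lists. This stands too, so step 3 is illustration only.

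A third reply is that .05 is the ordinary reading of significant. That may supply a p-value, but it supplies neither an effect-size threshold nor a variable list. If the word were instead read as related to outcome, the stated purpose of correcting nonequivalence would not fit, and the model would still depend on the data.

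A reader might go further and infer that the rule biases the treatment effect, inflates type I error or leaves the trial underpowered. The documents do not support this: applied mechanically, the rule does none of these. A reader might also expect a large power gain. A linear-model check gives 83%, 89% and 97% with prespecified adjustment, against 80%, 80% and 82% under the imbalance rule, for covariate–outcome correlations of 0.3, 0.5 and 0.7. The documents give no such correlation, and a linear model only approximates a count outcome.

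**Conclusion.** The concern holds at low-to-moderate severity. The primary utilization model is not fixed until data are seen, because covariates depend on chance imbalance judged by incomplete criteria. A given prognostic factor would be left out about 95% of the time at p<.05, and 76% or 98% at the two assumed effect-size cut-offs.

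The certain cost is analyst discretion in the primary model, whichever term is tested. The conditional cost is precision. If the group rate ratio over follow-up is the primary test, as the sample size wording suggests, always adjusting lowers the SE by about 1–4% and gains about 1–3 power points for a covariate with rate ratio 1.3–1.5 per SD. An upper-end covariate (1.8 per SD) would gain 3.2–6.4 points. These figures rest on assumed event rates, dispersion and covariate strength. If group-by-time is the primary test, the loss is essentially nil and the benefit of a change is a fixed, reproducible model.

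**What to change.** - Drop balance testing as a selection rule, and show baseline tables descriptively.
- Before data are seen by arm, name a short list of prognostic covariates that are already collected and measured before assignment. Include it in the primary utilization model whatever the observed balance. Candidates are age, number of cardiometabolic conditions, and prior admissions if the baseline chart audit records them.
- Do not use the final length of the index stay, although length of stay is on the baseline chart-review list. Patients are assigned while inpatient and the nurse component starts in hospital, so the stay ends after assignment and the intervention could affect its length.
- Screener results precede consent and so qualify on timing. The documents do not say whether the baseline interview precedes disclosure of assignment, so confirm this before listing any patient-reported measure.
- State whether the group rate ratio over follow-up or group-by-time is the primary test.
- Report the unadjusted estimate as a sensitivity analysis.

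The cost is SAP wording, a few degrees of freedom and an early commitment to the list. The documents do not show which variables predict utilization, so a poor list gains little precision, but the model is still fixed. With a log link the rate ratio keeps its meaning after adjustment. With a logit link for a yes/no readmission outcome, the adjusted odds ratio is conditional and should be labelled so.
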